22.3.3 General Statistical Methods

Appropriate summary statistics will be calculated and reported to describe the overall study results. Confidence intervals will be calculated as needed to assess the degree of precision in estimates. Approximate significance (α) levels of 5% will be used in statistical tests and confidence intervals.

Data tabulations and summarization will be presented to aid in the interpretation of the effects of clinically significant variables that are disclosed. Summary of continuous variables will be summarized using mean, SD, minimum, and maximum; categorical variables will be summarized as counts and percentages.

Appropriate parametric and/or non-parametric analyses will be chosen for statistical analysis. Test of association for the table of counts will be based on the Fisher's Exact Test unless otherwise noted.

Continuous variables will be analyzed using t-test and ANOVA if appropriate. Otherwise, the hypothesis of location for these measurements will be tested using Wilcoxon rank-sum or Kruskal-Wallis tests.

Time course distribution of Adverse Events for the safety population will be tabulated. Analysis of revision status will be using test of proportion such as Binomial test and Fisher's Exact test unless otherwise inappropriate.

A listing will be created to present all the data collected during the study.

22.3.4 Missing Data

A Patient accountability table, along with the explanation for lost-to-follow-up, death, revision, and withdrawn patients, will be provided in the final study analyses.

22.4 Adverse Events

Time course distribution of Adverse Events for the safety population will be tabulated. Analysis of revision status will be done using a test of proportion such as Binomial test and Chi-square test unless otherwise noted. Additionally, the safety of R3 ODH-ODH will be assessed by analyzing the revision rate at 6 months, two years, 5 years, 7 years and 10 years post-operatively as well as by applicable operative and post-operative adverse events (device related or otherwise). Kaplan-Meier estimates will be used to analyze the survivorship of the prosthesis. For survivorship analyses, revision of one or more components will be defined as failure.

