22.2 Sample Size

A total of 25 subjects will be enrolled (20 ODH-ODH and 5 controls) in the study and all must reach their 6 month follow-up interval.

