## 5. Statistical Considerations

### 5.1 Determination of Sample Size

A total of 25 subjects were enrolled in the study (20: ODH-ODH and 5 controls). All patients completing the 2 year primary follow up were invited to participate in the extension phase of the study. No justification for the sample size was provided.

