### 6.9.1 Device-Related Revisions

The Kaplan-Meier product limit survival estimates will be presented at 6-months, 2-years, 5-years, 7-years and 10-years post-op along with the associated 95% confidence intervals. The event of interest will be device-related revisions. Subjects who do not have device-related revision will be censored either at the time-point being analysed i.e. 5-years at the 5-year interim analysis etc. or at the time they discontinue from the study for

Statistical Analysis Plan	
A Consecutive Series Pilot Study Evaluating the Safety and Effectiveness of a New Hard-on-Hard Total Hip Replacement System in Patients with Non-inflammatory Arthritis with a Standard THA Metal Ion Control Group	Number: 2011-ODHH166
	ST: 1040
	Version: V1.0 26-Nov-2018
	Page: 11 of 13

any other reason i.e. lost to follow-up. This analysis will be presented by treatment (control/ R3 ODH-ODH).

The Kaplan Meier Survival plot will also be presented at 12 months both overall and by device type.

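### Protocol 22.3.3 and 22.4 name different tests for revision status, and the chi-square test in 22.4 is not valid for groups of 20 and 5 (minor)

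*Protocol*

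**What the plan says.** Revision is part of the primary safety outcome (Protocol 3.1; SAP 4.1). The protocol describes its analysis twice:

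- Section 22.3.3: "Analysis of revision status will be using test of proportion such as Binomial test and Fisher's Exact test unless otherwise inappropriate".
- Section 22.4: "Analysis of revision status will be done using a test of proportion such as Binomial test and Chi-square test unless otherwise noted".

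Section 22.3.3 also sets a default for count tables: "Test of association for the table of counts will be based on the Fisher's Exact Test unless otherwise noted". On the level of testing it says: "Approximate significance (α) levels of 5% will be used in statistical tests and confidence intervals". SAP 6.1 makes tests two-sided at 5%.

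On group sizes, Protocol 22.2 says: "A total of 25 subjects will be enrolled (20 ODH-ODH and 5 controls) in the study". SAP 5.1 reports the same numbers as enrolled and states that the sample size was not justified.

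SAP 6.9.1 plans Kaplan-Meier estimates of device-related revision with 95% confidence intervals at 6 months and at 2, 5, 7 and 10 years. It adds: "This analysis will be presented by treatment (control/ R3 ODH-ODH". It names no test of proportions and does not refer to the tests in the protocol.

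**The concern.** The binomial test is common to both sentences, so the conflict lies between Fisher's exact test and chi-square. The default in 22.3.3 does not settle it: that default yields where something else is noted, and 22.4 can be read as such a note.

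The choice matters because the groups are very small and unequal and few revisions are expected. Expected counts below 1 are then unavoidable, and the chi-square approximation cannot be relied on. At stake is whether a single revision among five controls could be called a significant difference in favour of the new device, depending on which section an analyst follows.

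**Working it through.** The documents give no p-value, power or assumed revision rate for this endpoint, so there is no figure of theirs to reproduce.

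**Inputs.** Group sizes 20 and 5 (Protocol 22.2, SAP 5.1); two-sided 5% (SAP 6.1). The common revision rates of 2% to 20% used below are assumptions.

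**One control revision, none in ODH-ODH (0/20 v 1/5).**

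- Expected revisions: 20 × 1/25 = 0.8 and 5 × 1/25 = 0.2.
- Uncorrected Pearson, N(ad − bc)² / (product of the four margins): 25 × (0×4 − 20×1)² / (20 × 5 × 1 × 24) = 10,000 / 2,400 = 4.167, p = 0.041.
- With Yates correction: 25 × (20 − 12.5)² / 2,400 = 0.586, p = 0.444.
- Fisher: the chance that the one revision falls among the controls is 5/25, so p = 0.200.

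**Other tables.**

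| ODH-ODH v control | Pearson p | Yates p | Fisher p |
|---|---|---|---|
| 0/20 v 1/5 | 0.041 | 0.444 | 0.200 |
| 1/20 v 2/5 | 0.031 | 0.166 | 0.091 |
| 0/20 v 2/5 | 0.003 | 0.043 | 0.033 |
| 1/20 v 0/5 | 0.610 | 1.000 | 1.000 |
| 0/18 v 1/5 | 0.052 | 0.484 | 0.217 |

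Fisher check for 1/20 v 2/5: (10 × 20 + 10) / 2,300 = 0.091. For 0/20 v 2/5: 10/300 = 0.033.

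**Actual size at nominal 5%.** For a common rate r, sum Binomial(20, r) × Binomial(5, r) over all tables with p < 0.05. Tables with no revisions at all count as non-rejections.

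| Assumed r | Uncorrected Pearson | Yates | Fisher |
|---|---|---|---|
| 2% | 6.5% | 0.3% | 0.3% |
| 5% | 9.0% | 0.9% | 0.9% |
| 10% | 7.6% | 1.2% | 1.5% |
| 15% | 5.8% | 1.1% | 1.7% |
| 20% | 4.7% | 1.0% | 1.9% |

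At low rates the excess comes mainly from the single table 0/20 v 1/5. At r = 2% its probability is 0.98²⁰ × 5 × 0.02 × 0.98⁴ = 0.0616, out of the total 0.065.

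**The case against.** A reader might infer that one control revision would be reported as a significant advantage for the new device. The documents do not support that, for these reasons:

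- **Permissive wording.** Both sentences offer tests as examples and carry an exception. Neither mentions controls or a comparison between groups, and 22.4 goes on to discuss the revision rate of R3 ODH-ODH alone. The between-group comparison that Protocol 22.1 and 22.3.1 describe is of metal ions.
- **Role of the controls.** Section 22.3.1 says that in the 2-year study controls give blood only and stay out of the overall analysis. It describes the 5-, 7- and 10-year analyses in terms of descriptive statistics.
- **The later SAP.** Dated November 2018, after the January 2017 amendment, it gives Kaplan-Meier estimates with intervals and no comparative test of revision. Where it wants tests, as for HHS and HOOS, it names them.
- **A fragile p-value.** The figure of 0.041 needs the uncorrected form and almost complete data. Yates correction removes it, and with two ODH-ODH subjects missing (18 v 5) it becomes 0.052.
- **Inflation is not universal.** It depends on assumed rates and has gone by 20%.

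All of this stands and limits the weight of the point. It does not remove the conflict: the two protocol sentences still differ, the chi-square form is unspecified, and the SAP presents revision by treatment without saying that the protocol's tests no longer apply.

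**Conclusion.** The inconsistency is real and minor. Two current sections name different tests for a primary endpoint, with no order of precedence. The chi-square test in 22.4 would be invalid for a comparison of 20 with 5.

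If such a test were run in uncorrected form on complete data, one control revision and no ODH-ODH revision could be called significant where Fisher's test gives p=0.200. The reverse single event, one ODH-ODH revision and none in controls, is non-significant under either test.

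The conclusion is conditional on someone choosing to run a between-group test. The SAP does not plan one, and no stated hypothesis or decision rule depends on it. The size figures rest on assumed revision rates; the p-values rest only on the group sizes.

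**What to change.** Either of two one-sentence changes is enough:

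1. In Protocol 22.4, replace the chi-square test with Fisher's exact test, to match 22.3.3.
2. In SAP 6.9.1, state that revision is described by Kaplan-Meier estimates with 95% confidence intervals only, that no between-group test will be run, and that this supersedes Protocol 22.3.3 and 22.4 on this point.

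The second fits what the SAP already plans and avoids a protocol amendment, which needs ethics committee approval under Protocol 6.0. The cost of the first is conservatism: at the assumed rates Fisher's actual size is 0.3% to 1.9%, and with no ODH-ODH revision it would take two control revisions to reach p < 0.05 (p=0.033). Neither change needs new data.

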22.5 Site Selection

Investigators are selected by the Sponsor and selection is based on the training of the Investigator, the ability of his/her site to enroll an expected number of subjects in a reasonable period of time, the commitment to conduct the study according to the protocol, the ability to control investigational inventory, and other Sponsor stipulations and applicable regulatory requirements. The Investigators were selected because they have been instrumental in the design and development of the protocol from the early stages, and for their knowledge of the device. Investigators who have been sanctioned by regulatory agencies may not participate in the study.

23.0 Monitoring Procedures

23.1 Direct Access

This study will be monitored by the Sponsor or a qualified person designated by the Sponsor. This qualified person could be an employee of the Sponsor or of a contract research organization (Sponsor's agent). Documentation that the monitor has been trained will be maintained.

The Investigator will provide to Sponsor, Sponsor's agents, IEC and regulatory agencies direct access to all source data/documents to permit study-related monitoring, audits, IEC review, and regulatory inspections.

23.2 Pre-study

A site qualification visit will be performed by the Sponsor or CRO prior to the execution of a clinical agreement to ensure that all Investigators have the appropriate training, staff, facilities and resources to adequately conduct the study.

A site initiation visit will be performed by the Sponsor following the execution of the clinical agreement and documented IEC approval to provide training to the site on the specifics of the study and its conduct.

23.3 Interim Monitoring

The Sponsor or CRO will perform interim monitoring visits on a regular basis according to a schedule determined by the Sponsor. During these visits, the monitor will verify:

- the informed consent process occurred and is documented appropriately
- all inclusion/exclusion criteria were met
- source documentation is complete and available
- the data on CRFs is verified by the source documentation
- compliance with the protocol
- the reporting of adverse events occurred as required
- all required study documentation is complete and available

23.4 Closeout Visit

A study-close out visit will be performed by the Sponsor or CRO to retrieve and account for all remaining clinical data and investigational products. During study close-out, the monitor will review all Investigator files to ensure all required documents and records are on file, confirm the disposition of the investigational products and any other ancillary items used for the study, and review regulatory requirements regarding records retention and IEC reporting requirements. Any remaining investigational inventory will be collected and returned to the Sponsor at the end of the 10 year follow up if it was not collected following the enrollment period.

23.5 Documentation of Monitoring Visits

All activities associated with a monitor visit will be documented. This includes:

- Monitor visit log on site
- Monitor visit notification letter
- List of charts and/or hospital charts that were reviewed
- Review of the administrative binder
- Description of any site deficiencies
- Site compliance with protocol
- Description of any protocol deviations
- Assurance that informed consents were obtained and IEC review is current
- Device accountability
- Review of findings with available site personnel

All findings from the monitoring visit will be documented in a letter to the Investigator after the visit. Any site deficiencies will be noted and action items will be listed.

24.0 Risk Analysis

24.1 Risk and Precautions

Surgery Related Risks

The adverse events listed below can occur as the result of all THR surgery regardless of the specific device utilized:

- revision
- particulate wear debris generation
- device wear particle induced osteolysis, inflammation, etc.
- osteolysis or other bony abnormalities (including ectopic or heterotopic bone formation) as a result of wear, debris generation, or other causes
- loosening, bending, cracking, fretting, corrosion, stress shielding, dislocation, subluxation, improper loading, fracture of implant components, squeaking, clicking, stiffness, impingement, or mis-alignment
- worsened pain, function, range of motion, or change in limb length
- bone fracture
- difficulty implanting prosthesis components
- superficial or deep wound infection occurring early or late
- nerve injury resulting in transient or permanent motor and or sensory deficits
- wound hematoma and thromboembolic disease
- periarthritis calcification disorders
- pseudotumors
- trochanteric nonunion (when a transtrochanteric surgical approach is used)
- allergic reaction to materials in the implants
- large blood vessel damage and possible large blood loss (> 1500 ml) necessitating transfusion
- traumatic arthrosis from intraoperative positioning of the extremity
- delayed wound healing
- ipsilateral or contralateral limb problems due to length discrepancy, improper alignment, or muscle deficiency
- unsuccessful arthroplasty or failure to relieve symptoms.

Other adverse events are possible including death. These are events that may be reasonably expected to occur given a large enough subject population. A subject can experience almost any complication depending on the individual's circumstances. The frequency and severity will be a determining factor in assessing the importance of any specific event occurrence not listed.

In addition to general surgical risks, the risks listed below may occur as the result of treatment with the R3 ODH-on-ODH Hip System:

- Higher than normal wear of the ODH material may occur
- Allergic reaction to the material used in the implants
- Temporary or permanent device related noise such as clicking or squeaking
- Other unknown risks associated with the new material used in the device

24.2 Study Related Risks

Risks that may occur as a result of study research procedures include:

- Radiologic Exposure
- Pain and bruising and possible infection at the site of blood draw
- Loss of confidentiality

24.3 Manner in Which Potential Risks will be Minimized

The risk of loss of privacy will be mitigated by following Good Clinical Practice (GCP) compliant procedures to manage patient confidentiality and study operations. Patients will be identified by the assigned patient number on Case Report Forms (CRFs) and other documents submitted to the Sponsor. Documents that will not be submitted to the Sponsor and that identify the patient (e.g., the signed informed consent form) will be maintained in strict confidence by the site Investigator, except to the extent necessary to allow auditing by the appropriate ethics authority and the study monitor.

The coupling portion of the investigational device is made of Zirconium and Niobium. Other elements are trace. There are no known adverse health effects of exposure to Zirconium and Niobium. Pregnant women should avoid exposure to increased levels of metal ions. Pregnancy and planned pregnancy is an exclusion criterion for this study. In order to collect data about possible risks associated with metal ion release we will measure blood metal ion levels according to the assessment schedule.

Pseudotumor formation has been described in some cases of metal-on-metal prostheses. Risk of pseudotumor formation for this investigational device is unknown. Monitoring of pseudotumor formation will be conducted using study procedures for AE capture and through regular clinical monitoring of patient progress and radiologic imaging.

Some radiologic evaluations used in this study are not considered standard of care. Study-related radiologic exposure does not pose significant general health risk due to use of plain radiographs associated with low radiation levels. Pregnant women should not receive radiologic- assessments. Pregnancy and planned pregnancy is an exclusion criterion for the study. If a patient becomes pregnant during the course of this study, the patient will not participate in radiographic study assessments. Other study assessments and evaluations will continue according to the assessment schedule. The patient will resume radiographic assessments once pregnancy has ended. If the patient consents, the patient may be followed to obtain information about the pregnancy and outcome of the pregnancy.

Risk of pain and bruising and possible infection at the site of blood draw will be reduced by utilizing technicians that are trained in phlebotomy.

All Adverse Events will be reviewed on an ongoing basis by the Sponsor. Sponsor will review all adverse events to identify unanticipated device-associated adverse events.

The surgeon and manufacturer have proper experience, training, and device testing to support the use of the current device. The Investigators in this study have extensive

experience. The manufacturer is a large device company with a good track record of designing and producing quality orthopaedic products. Mechanical testing demonstrated the device will withstand in vivo requirements based on known factors. These efforts provide a superior risk minimization effect.

Adequate preclinical and mechanical testing and maintenance of quality manufacturing procedures (homogeneous composition, processing and design tolerances) combined with the history of prior use in other countries provides an excellent foundation on which to base the study of this type of device in a human clinical study. Careful attention to subject selection criteria and surgical implantation techniques may reduce the potential that components are exposed to forces that they were not intended and are aligned and seated properly. No guarantees can be made as to the success of this THA system.

24.4 Potential Benefits

Participation in this study may offer no direct benefit to subjects. However, most artificial joint replacement surgeries including THR surgery will allow a subject to have less pain, increased mobility, and the decreased use of medicines for pain especially early after surgery. The benefits of the study device should be compared with risks and benefits of other types of artificial joint replacement devices.

24.5 Justification for the Investigation

Investigation of the study device is justified because of its similarity to other commercially available arthroplasty devices, along with the possible benefits of reduced wear and particulate generation, in addition to reduced periprosthetic metal ion accumulation.

25.0 Investigator Responsibilities

The Investigator is responsible for ensuring that the investigation is conducted according to the Investigator Agreement, this Investigational Plan and applicable regulations as required. Investigator responsibilities are defined in ICH E6 GCP guidelines.

25.1 Investigator Records

The Investigator will maintain complete, accurate and current study records, including the following materials:

- Correspondence with the Sponsor, the Clinical Monitor, other Investigators, the IEC, or regulatory authorities
- Accountability of records or receipts:
- The use and disposition of all investigational devices and study materials
- The type and quantity of the device, the dates of its receipt, and the batch number or code mark;
- The names of all persons who received, used, or disposed of each device; and

- The number of devices that have been repaired, returned to the Sponsor, or otherwise disposed of, and the reason for such action;
- Study Subject Records including signed and dated informed consent forms, all source documentation, subject CRFs, queries and records of exposure of each subject to the device;
- All relevant observations, including records and reports concerning adverse effects (whether anticipated or unanticipated);
- Current study protocol and protocol deviation log, with dates and details of any reason for deviations from the protocol that could affect the scientific quality of the study or the rights, safety, or welfare of the subjects;
- The approved blank Informed Consent form and blank Subject CRFs;
- Certification that the Investigational Plan has been approved by all of the necessary approving authorities; and
- Signed Investigator Agreements with CV's of the Principal Investigator and any participating Co-Investigators attached updated at least annually.

25.2 Retention of Records

The Investigator must retain essential study documents until at least 2 years after the last marketing approval of the investigational product in an ICH region, or 15 years after the conduct of the study is complete, or for a longer period if required by the applicable local laws. The Investigator must obtain written permission from the Sponsor prior to destroying or moving study documents.

If an Investigator is unable to hold these records in his or her archives, the Investigator must make alternative arrangements. If an Investigator leaves the institution at which the study was conducted, another responsible party must be designated to maintain the records. Details of these arrangements must be documented in writing to the Sponsor.

25.3 Investigator Reports

The Investigator will be responsible for the following reports:

Adverse Event Reports: As described in this protocol.

Withdrawal of IEC Approval: The Investigator shall report to the Sponsor within 5 working days if, for any reason, the IEC withdraws approval to conduct the investigation. The report will include a complete description of the reason(s) for which approval was withdrawn.

Modification of the Protocol: Neither the Investigator nor Sponsor will modify this protocol without mutual agreement. After agreement to initiate the modification (in the form of a protocol amendment), the Investigator agrees not to institute this modification until instructed to do so by the Sponsor. It will be necessary to obtain IEC approval prior to implementation of any change in the protocol that may affect the scientific soundness or

the rights, safety, or welfare of the subjects involved. Notification shall be submitted to the IEC in no later than 5 working days.

Protocol Deviations: Protocol deviation is defined as any non-adherence to the protocol. Protocol deviations will be reported to Smith & Nephew. The Investigator must also report protocol deviations to the IEC as required by the IEC. Depending on the nature of the deviation, a decision will be made by the Investigator and Sponsor about whether the patient (for whom the departure from protocol was affected) is to continue in the study.

Implant of Device without Informed Consent: No Subject may be treated with the device without prior Informed Consent. Such treatment constitutes a violation of the study protocol. The Investigator shall submit a report indicating the circumstances for the occurrence to Smith & Nephew and to the reviewing IEC within five working days after the use occurs.”

Progress Reports: The Investigator is required to submit six bi-monthly progress reports to the study Sponsor and to the reviewing IEC. Reports must include the number of subjects, a summary of all follow-up evaluations, and a general description of the study's progress.

Final Report: The Investigator will submit a final report to the Sponsor and to the IEC within 3 months of termination of the study, the termination of the Investigator's participation in the study, or at the completion of the study.

Other Reports: Upon request of the Sponsor or the IEC, the Investigator shall provide accurate, complete and current information.

